E4. Neonates

Will neonates of uncertain viability or nonviable neonates (as described in 45 CFR 46 Subpart B) be enrolled in the research?

No

E5. Children

Will children be enrolled in the research?

No

Section F: Design/Procedure

F1. Design

Select one category that most adequately describes your research:

c) Pilot

Discuss the research design including but not limited to such issues as: probability of group assignment, potential for subject to be randomized to placebo group, use of control subjects, etc.

We will prospectively recruit 40 patients at risk of ICUAW. Sample size is convenient and designed to explore acceptability and feasibility of objective tools for measurement. Eligible participants will be screened at BSLMC. Those who satisfied the inclusion and exclusion criteria and signed the informed consent form will be randomly assigned with ratio of 1:1 into two groups. Consenting will be performed with a legal authorized representative (LAR) that is present. When the subject regains consciousness and is aware in time, space, and person, he/she will be re-consented. If the subject decline to continue participation in the study, the subject will be withdrawn. The informed consent will be obtained from all participants and their LAR.

Sub-population: Post-surgical patients that are admitted to the ICU will be consented either before surgery, or by a LAR on the day of surgery as described above.

The study will be double-blinded (clinicians and patients) in intervention (IG) and control (CG) group. Both cohorts will be followed-up and monitored at 3 days, and then weekly for a total period of 4 weeks or until hospital discharge, whichever comes first. • Intervention group (IG). The IG (n=20) will be undergoing E-Stim therapy with an active device during the hospitalization period until 4 weeks or discharge, whichever comes first. To deliver E-Stim, 2 electrodes will be placed in each proximal gastrocnemius and Achilles tendons. • Control Group (CG). The CG (n=20) will be undergoing E-Stim therapy with a placebo device (5-10% currents) as described in the IG.

Inclusion Criteria:

-Any patient older than 18 years old admitted to the ICU within two days. -Patient can be intubated with ventilatory assistance or not.

Exclusion Criteria:

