Neuropathy test: Sural nerve conduction/amplitude assessment (neuropathy, DPNCheck Device by Neurometrix Inc)

Biomarkers tests: Creatinine kinase, C-reactive protein, creatinine, potassium, myosin, serum lactate, arterial SpO2, duplex ultrasound for DVT will be collected from the electronic medical records. If biomarkers were not collected as a standard/regular procedure in the ICU; data will not be extracted from the electronic medical records. Research staff will not draw any blood samples.

Then, the patients will receive an individually programmed device to deliver neuromodulation to both gastrocnemius muscles simultaneously. The frequency of therapy will be 1 hour daily, and the duration will be up to 4 weeks or until hospital discharge, whichever comes first.

The coordinator will provide the ICU staff with a weekly spreadsheet showing utilization (therapy sessions/day) so compliance can be monitored. Also, the devices will monitor the time of usage to confirm hours of effective neuromodulation therapy to the skin.

Follow-up assessments will be performed at 3 days, and then weekly until 4 weeks or until hospital discharge, whichever comes first, by the research staff. The follow-up assessment will be identical to the baseline assessment.

In the final visit, we will assess muscle strength (ankle dynamometer, RoMech Digital Hanging Scale).

Additional measurements: - 1-month post-hospital discharge phone questionnaires: instrumental activity of daily living scale (IADL), community engagement (the Life Space Questionnaire), independence in daily living activities (KATZ), and anxiety (BAI).

Section G: Sample Size/Data Analysis

G1. Sample Size

How many subjects (or specimens, or charts) will be used in this study?

Local: 40 Worldwide: 40

Please indicate why you chose the sample size proposed:

Sample size is convenient and selected based on available resources to demonstrate feasibility and the proof of concept effectiveness of neuromodulation therapy for patients admitted to ICU and post-ICU. We plan to recruit 40 eligible subjects.

G2. Data Analysis

Provide a description of your plan for data analysis. State the types of comparisons you plan (e.g. comparison of means, comparison of proportions, regressions, analysis of variance). Which is the PRIMARY comparison/analysis? How will the analyses proposed relate to the primary purposes of your study?

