Statistical Design: Independent t-test, U-test, or Chi-square (depends on type of variables) will be used to compare between groups (IG, and CG for key baseline descriptors including demographics and relevant clinical characteristics). Those descriptors which showed statistical significant difference will be considered as covariates for adjusting the results in the following assessments. Appropriate mixed models (linear for continuous or Generalized Estimating Equations (GEEs) for non-continuous or non-parametric variables) will be used to test the intervention effect for each of the primary or secondary outcomes. Results will be adjusted by covariates as described above.

P-values of 0.05 or less will be considered statistically significant based on a two-sided test unless otherwise noted. All variables will be tabulated descriptively at each scheduled time point (baseline, follow up and discharge date). For each continuous variable, the analyses will include the mean, standard deviation, minimum and maximum. For each categorical variable, the summary will include frequencies and percentages. Each variable will be analyzed using all available data. Baseline variables will be summarized using descriptive statistics. We assume that a successful intervention is also helpful to maintain subjects muscle mass, reduce neuromyopathy signs and increase perfusion. The measured parameters (e.g. sEMG, US, strength, Kent imaging, DPN Check, etc.) should change substantially from baseline to the end of the intervention. For example, the EMG amplitude values should show increased voltages. Next, for all continuous variables, pre-treatment scores will be regressed on post-treatment scores to form residualized change scores (e.g. sEMG, US, strength, Kent imaging, DPN Check, etc.). Correlations will then be generated among these scores to determine whether changes in sEMG factors are related appropriately with increases in (clinically assessed) functional capacities and self-report measures of activities at 1 month post-hospital discharge. ANOVA test will be used to examine significant difference between patients with severe risk factors for prolonged ICU stage (e.g. age, BMI, cardiovascular morbidities). Moderator effects will also be examined for exploratory purposes.

Section H: Potential Risks/Discomforts

H1. Potential Risks/Discomforts

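### GEE is planned for non-continuous and non-normal outcomes with 20 patients per arm and no small-sample correction; a cheap wording change would keep its tests close to the stated 5% level.

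*Combined protocol and SAP*

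**What the plan says.** Section G2 gives continuous outcomes a linear mixed model and uses "Generalized Estimating Equations (GEEs) for non-continuous or non-parametric variables". Section I repeats the rule. It covers the primary and secondary outcomes alike.

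The significance rule is "P-values of 0.05 or less will be considered statistically significant based on a two-sided test unless otherwise noted". On incomplete data the plan says only "Each variable will be analyzed using all available data".

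Section F1 (Design) sets the size and schedule: "We will prospectively recruit 40 patients at risk of ICUAW", "randomly assigned with ratio of 1:1 into two groups", and "followed-up and monitored at 3 days, and then weekly for a total period of 4 weeks or until hospital discharge". Section G1 explains the number: "Sample size is convenient and selected based on available resources".

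The plan does not state the GEE working correlation, variance estimator, reference distribution or tested contrast. It states no assumption about missing visits and no expected number of patients still in hospital at each visit.

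**The concern.** A variable is not itself non-parametric. Because non-continuous variables are listed separately, the most natural reading of that clause is continuous variables that are not normally distributed. Creatine kinase and C-reactive protein are obvious candidates. sEMG or sural amplitude could follow if judged non-normal.

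Two properties of GEE then matter.

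- **Error rate.** The ordinary sandwich variance is too small when there are few patients, and a normal reference adds to the excess. At 20 per arm the effect is modest. It grows as patients are discharged.
- **Bias.** Unweighted GEE on available data is in general valid only if being discharged is unrelated to outcome. Discharge after intensive care may well follow recovery, and Section I says the study will examine whether the therapy shortens the stay.

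At stake are the meaning of a p-value below 0.05 for these outcomes and the size of any difference reported at the later visits.

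**Working it through.** **Inputs from the plan.** Two-sided level 0.05 (G2); 20 per arm, 1:1 (F1); post-baseline visits at day 3 and weeks 1 to 4, ending at discharge (F1, F2). The sample size has no power calculation behind it, so the only figure to compare against is the 5% level.

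**Assumed, not in the plan.** An uncorrected sandwich variance with a normal reference, and a 0%, 15% or 25% chance of discharge per interval. Over the four intervals from day 3 to week 4 this leaves 20 × 0.85⁴ = 10.4 or 20 × 0.75⁴ = 6.3 per arm.

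**Step 1: closed form, one visit, normal data, n per arm.** Let s² be the pooled variance.

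- The usual squared standard error is 2s²/n, which gives a t statistic T on 2n−2 degrees of freedom.
- The uncorrected sandwich gives 2s²(n−1)/n², so its z equals T·√(n/(n−1)). True level = 2·P(t₂ₙ₋₂ > 1.96·√((n−1)/n)).
- Mancl-DeRouen divides each residual by 1−1/n and gives 2s²/(n−1). True level with z = 2·P(t₂ₙ₋₂ > 1.96·√(n/(n−1))). With a t reference, replace 1.96 by the 97.5% point of t on 2n−2 degrees of freedom.

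Example, n = 20: 1.96 × √(19/20) = 1.910, and 2·P(t₃₈ > 1.910) = 6.4%.

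| n per arm | Sandwich, z | Mancl-DeRouen, z | Mancl-DeRouen, t |
|---|---|---|---|
| 20 | 6.4% | 5.2% | 4.5% |
| 10 | 7.9% | 5.4% | 4.0% |
| 7 | 9.5% | 5.6% | 3.7% |
| 5 | 11.8% | 6.0% | 3.3% |

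**Step 2: simulated error rate, full GEE.** There were 20 per arm and five post-baseline visits, with baseline adjustment for normal and skewed outcomes and independence or exchangeable correlation. Each setting had 2,800 null trials (Monte Carlo standard error about 0.4 to 0.6 points). The week-4 level of the sandwich z test, normal and skewed outcomes together, was:

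- no discharge: about 5.5% to 7%;
- 15% per interval: about 6.5% to 9%;
- 25% per interval: about 10% to 12%. Here Mancl-DeRouen gave about 4.5% to 7% with z and 2% to 4% with t.

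A joint five-degree-of-freedom test over all visits was worse: about 10% to 14% with no discharge and 14% to 25% at 25%. Mancl-DeRouen left it at about 7% to 15%, so the choice of contrast matters.

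**Step 3: binary outcomes (600 trials per setting, no baseline adjustment).** The direction is mixed. Under independence the week-4 level was 4.8% with no discharge, 2% to 3.4% at 15%, and 0% at 25% with 39% of fits failing. Under exchangeable correlation it was 4% to 6% at 15% and 8.6% at 25%.

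**Step 4: bias at week 4 (600 trials per setting).**

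- No effect and the same discharge process in both arms: centred on 0.
- Skewed outcome, real effect, discharge depending on the last observed value: estimates of 0.52 to 0.76 against a full-data difference of about 1.05 to 1.09, that is 30% to 51% too small.
- The same effect with discharge unrelated to outcome: 1.05 to 1.10 against 1.05 to 1.08, so no bias.
- Normal outcome, outcome-dependent discharge: exchangeable 0.99 to 1.03 against 0.97 to 1.03; independence 1% to 12% too small.
- Heavier discharge (about 4.2 per arm left at week 4), normal outcome: independence gave 0.59 against 0.78, and (0.78 − 0.59)/0.78 = 24% too small. Exchangeable stayed close to the truth.

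**The case against.** A reader might infer that late-visit GEE tests in this trial will exceed 5% and that their estimates will be biased. The documents do not support that as a certainty, for these reasons.

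- **Which outcomes.** G2 itself names sEMG, ultrasound, strength, Kent imaging and DPN Check as examples of continuous variables. By the plan's own rule they go to the linear mixed model unless later judged non-normal. What clearly remains for GEE is mainly biomarkers, taken only when routine care recorded them, and binary items.
- **Which test.** G2 plans a test of the intervention effect, not a GEE test at each visit. Comparison by time point is stated only for perfusion, which G2 treats as continuous. In a simulation of normal data the overall group effect was only slightly inflated.
- **Which endpoint.** Aim 2 is set at four weeks or discharge, whichever comes first. An end-of-intervention contrast could include patients discharged early and would not shrink to those still in hospital.
- **Which software choice.** The plan names no variance estimator, so the uncorrected sandwich is an assumption, though a usual one.
- **Which direction.** Sparse binary outcomes tended to under-reject or fail to converge.
- **Setting.** This is a pilot with a convenience sample.

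All of this stands and limits the point to a conditional one. It does not remove it. G2 still declares significance at 0.05, the level is above 5% even at 20 per arm under the usual sandwich z test, and a better option costs almost nothing.

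**Conclusion.** The point holds as a cheap improvement. With the uncorrected sandwich error and a normal reference, a continuous outcome sent to GEE is tested at about 6.4% with all 20 per arm. At a visit where 10 to 5 per arm remain, the level is about 8% to 12%. The first figure needs no discharge assumption; the second does, and the documents give no rate. The inflation mainly concerns non-normal continuous outcomes. It should not be extended to sparse binary outcomes, or to the named primary measures while they stay in the linear mixed model.

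Understatement of late-visit differences needs a real effect and discharge that depends on observed recovery. Under both, it was clear for skewed outcomes (30% to 51% in the settings tried) and small for near-normal outcomes with exchangeable correlation.

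**What to change.** In G2, and where Section I repeats the rule:

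1. Drop the non-parametric category from the GEE clause. Keep skewed continuous outcomes, suitably transformed (for example by logarithm), in the linear mixed model, fitted by REML with Kenward-Roger degrees of freedom, with baseline, arm, visit and arm-by-visit terms. A likelihood-based model also copes better with discharge that depends on observed values, provided the model is adequate.
2. For truly non-continuous outcomes, use GEE with a Mancl-DeRouen variance and a t reference and state the working correlation, or use a mixed logistic or ordinal model.
3. Name the tested contrast for each outcome. Prefer a single-degree-of-freedom contrast, because the correction did not bring the joint test of all visits to 5%.
4. Report late-visit GEE estimates as descriptive, with the number still in hospital per arm. Weighting for remaining in hospital should be at most a sensitivity analysis: the weights would come from a handful of patients, and it was not tested here.

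The cost is a few sentences and standard software options. Intervals become slightly wider, and the t-referenced test is somewhat conservative (4.5% at 20 per arm, 3.3% at 5). Log-transformed outcomes are reported as ratios. The variance correction does not by itself remove bias from outcome-dependent discharge.

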Studies have reported a series of measurements to demonstrate the efficacy of E-stim therapy such as thigh circumference, strength of lower extremity muscles (isometric or isotonic dynamometry, MRC score), and quality of life questionnaires. In our previously mentioned trial (NCT04685213, H-47781-A), dynamometer tests were difficult to obtain due to patient sedation, medical paralyzation or intubation. Moreover, calf circumference was altered in patients with present edema. Even though we did not assess MRC score or quality of life questionnaires, lack of feasibility also applies for this measurements because it requires awareness of the patient. Therefore, objective measurements that do not depend or interfere with the patient status are needed to evaluate the progress/effectiveness of E-Stim therapy.

Quantitative neuromuscular ultrasound is emerging as a potential research and diagnostic tool but is not a clinical standard of care. Although creatinine kinase may be elevated in patients with ICUAW, there are no validated biomarkers used for diagnosing ICUAW. In our previous trials (NCT04685213, H-47781-A; NCT05198466, H-47781-B), surface electromyography (sEMG) has been able to detect muscle endurance in response to E-Stim. This parameter was associated with a decreased likelihood to fall at the time of ICU discharge, and an increase in muscle perfusion of Post-COVID-19 patients with neuromuscular sequelae. This suggests that sEMG can be an objective and feasible muscle assessment for ICU patients regardless of awareness. Moreover, Moss et al. reported that sural sensory nerve conductive assessment yielded a sensitivity of 100% with a specificity of 81% to diagnose neuromyopathy due to ICUAW. Therefore, we purpose to utilize a nerve conductive/amplitude assessment tool of the sural nerve called DPN Check device (Neurometrix Inc.).

Lastly, our institution has a high volume of intensive care units (N=10) (Baylor St Luke's Medical Center, Houston, TX, USA) supervised by specialists in critical, intensive, and post-surgical care. Therefore, we believe our institution is a suitable place to perform this study.

Section D: Purpose and Objectives

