Aim 1. Acceptability: To examine feasibility and acceptability of lower extremity neuromodulation in patients at risk of ICUAW. H1.1: The adherence to daily use of lower extremity neuromodulation is more than 80% among the IG. Adherence is defined as the use of lower extremity neuromodulation at least one hour per day for at least 4 days per week. H1.2: The perceived acceptability, and perceived benefit would be high among IG.

Aim 2. Proof of concept effectiveness: To examine effectiveness of lower extremity neuromodulation for intubated patients at risk of ICUAW H1.1: E-Stim will improve motor function including muscle endurance and thickness, nerve conductivity and amplitude, by utilizing objective assessments (surface electromyography, ultrasound, dynamometry), after 4 weeks of application or hospital discharge, whichever comes first. H1.2: E-Stim will improve lower extremity nerve function and tissue perfusion after 4 weeks of application or until hospital discharge, whichever comes first. The nerve function parameters will be measured with assessed with a digital test (DPN Check) for peripheral neuropathy and the perfusion parameters will be assessed using a near infrared spectroscopy using a validated imaging system (Kent Imaging System).

Section E: Protocol Risks/Subjects

E1. Risk Category

Category 1: Research not involving greater than minimum risk.

E2. Subjects

Gender:

Both

Age:

Adult (18-64 yrs), Geriatric (65+ yrs)

Ethnicity:

All Ethnicities

Primary Language:

English, Spanish

Groups to be recruited will include:

Patients

Which if any of the following vulnerable populations will be recruited as subjects?

Cognitively impaired

Vulnerable populations require special protections. How will you obtain informed consent, protect subject confidentiality, and prevent undue coercion?

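### Section G2 forms its residualised change scores the wrong way round and includes strength, which has no baseline

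*Combined protocol and SAP*

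**What the plan says.** Section G2 (Data Analysis) sets out a step that covers every continuous measure: "pre-treatment scores will be regressed on post-treatment scores to form residualized change scores (e.g. sEMG, US, strength, Kent imaging, DPN Check, etc"). The resulting scores are then correlated with one another to learn "whether changes in sEMG factors are related appropriately with increases in (clinically assessed) functional capacities and self-report measures" of activity one month after discharge. Just before this, G2 says: "The measured parameters (e.g. sEMG, US, strength, Kent imaging, DPN Check, etc.) should change substantially from baseline to the end of the intervention". Strength is therefore listed twice as a variable with a baseline.

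Section F2 (Procedure) lists the baseline battery: sEMG, muscle ultrasound, Kent imaging, DPN Check and chart biomarkers. Follow-up repeats that battery. Strength appears separately: "In the final visit, we will assess muscle strength (ankle dynamometer, RoMech Digital Hanging Scale"). The self-report instruments are also given once: "1-month post-hospital discharge phone questionnaires: instrumental activity of daily living scale (IADL), community engagement (the Life Space Questionnaire"), KATZ and BAI.

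Aim 2 H1.1 (Section D) counts dynamometry among the tools that will show improvement, "by utilizing objective assessments (surface electromyography, ultrasound, dynamometry), after 4 weeks of application or hospital discharge, whichever comes first". The background section reports that in the earlier ICU trial "dynamometer tests were difficult to obtain due to patient sedation, medical paralyzation or intubation".

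Treatment effects are handled apart from all this: mixed models or GEE "will be used to test the intervention effect for each of the primary or secondary outcomes".

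**The concern.** There are two defects and one ambiguity.

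- **Direction.** To regress A on B is to make A the response. The residual G2 describes is the part of baseline that the post score does not explain, which is not a measure of change.
- **Strength.** With one measurement at the final visit there is no pre-treatment score, so neither the change from baseline nor the residualised score can be computed.
- **Questionnaires.** They are not named in the change-score list. But G2 applies the step to all continuous variables and correlates the resulting scores with each other, so it is unclear that the single 1-month value is what enters.

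At stake is whether the correlations answer their own question, namely whether patients whose sEMG improves more also function better. With the score as defined, a true positive relation can shrink, vanish or change sign, and a relation that comes only from baseline sEMG can look like a relation with change.

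**Working it through.** The plan gives no expected correlation or power to reproduce, because N = 40 is a convenience sample. From the document: n = 40, two-sided 5% level, and the direction and timing described above. Assumed: all correlations below.

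**Notation.** Baseline X and post Y are standardised, with Y = rX + √(1−r²)·e. F is an outcome measured once (final strength or a 1-month questionnaire), g = corr(F, X) and ρ = corr(F, e).

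**The two scores.**
- Proper (Y on X): the residual is e, up to scale.
- As G2 defines it (X on Y): X − rY, which scales to W = √(1−r²)·X − r·e.

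It follows that:
- corr(W, Y) = r√(1−r²) − r√(1−r²) = 0
- corr(W, e) = −r
- corr(W, F) = √(1−r²)·g − r·ρ, where the proper score gives ρ

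**Outcome measured once.** Worked example with r = 0.5, g = 0.3, ρ = 0.5: 0.866 × 0.3 − 0.5 × 0.5 = 0.260 − 0.250 = +0.01.

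| ρ (true) | g | r = 0.3 | r = 0.5 | r = 0.7 |
|---|---|---|---|---|
| 0.5 | 0 | −0.15 | −0.25 | −0.35 |
| 0.5 | 0.3 | +0.14 | +0.01 | −0.14 |
| 0.5 | 0.5 | +0.33 | +0.18 | +0.01 |
| 0.3 | 0.3 | +0.20 | +0.11 | 0.00 |
| 0.3 | 0.5 | +0.39 | +0.28 | +0.15 |
| 0 | 0.3 | +0.29 | +0.26 | +0.21 |

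The sign reverses only when g < rρ/√(1−r²). For ρ = 0.5 that threshold is 0.16, 0.29 and 0.49 at r = 0.3, 0.5 and 0.7. If F depends only on the post-treatment level, the result is exactly zero, because W is uncorrelated with Y.

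**Both measures taken twice** (sEMG with ultrasound, Kent imaging or DPN Check). Assume the same r for both, baseline correlation b, change correlation ρ, and no correlation between baseline and change. Then corr = (1−r²)·b + r²·ρ. With ρ = 0.5 and r = 0.3, 0.5, 0.7:
- b = 0: 0.05, 0.13, 0.25
- b = 0.3: 0.32, 0.35, 0.40
- b = 0.5: 0.50 throughout
- b = −0.3: −0.23, −0.10, +0.09

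Simulation with 1,000,000 subjects agreed with the formulas to within 0.003; the ρ = 0 row rests on the formula alone.

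**At n = 40 with complete data** (simulated trials, two-sided 5% test):

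| r, g, ρ | Proper score, significant positive | Score as in G2 |
|---|---|---|
| 0.6, 0.3, 0.5 | 92% | 0.2% significant positive, 2.4% significant negative |
| 0.6, 0, 0.5 | 92% | 46% significant negative |
| 0.3, 0.5, 0.3 | 46% | 71% significant positive |
| 0.5, 0.3, 0 | 2% | 36% significant positive |

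The first row is a near-cancellation: the expected correlation is 0.8 × 0.3 − 0.6 × 0.5 = −0.06. The last two rows show the opposite failure, where baseline sEMG passes for change.

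**The case against.** The strongest reply is that this is a drafting slip. G2 names the intended quantity correctly and speaks of changes in sEMG, and swapping the two sides of a regression is a common error. An experienced analyst might simply do the right thing, and then none of the numerical harm occurs. That is plausible, but G2 is the only place where the step is defined, and an analyst who follows it literally computes the wrong variable.

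Second, reversal is not the general result. If both sides of the correlation are residualised, as G2's text suggests, the sign is usually kept and the estimate is attenuated; reversal there needs a negative baseline correlation. Against outcomes measured once, reversal needs g below the threshold shown. The 92% against 0.2% contrast is a single setting where the terms nearly cancel: at r = 0.3 and g = ρ = 0.5, the score in G2 is still significantly positive in 54% of trials. All of this stands. The figures are illustrations and should not be quoted as the expected effect.

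Third, strength could be reconciled the other way. Non-intubated patients are eligible and some patients consent before surgery, so a baseline test is possible for some. This is a real alternative, but it would give a baseline only in a selected subset, and F2 does not schedule one. It is also fair to say that Aim 2 can be answered by a between-arm comparison at the final visit, so rewording it is a matter of consistency. Likewise, using the single questionnaire value is the only workable reading.

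Finally, G2 gives these correlations no rank, and this is a 40-patient pilot. That limits the weight of the point but does not make the rule correct.

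**Conclusion.** The concern holds. As defined, the score does not measure change, and strength cannot be given a change score under the assessment schedule in F2. Nothing in the document corrects either point.

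The algebraic facts (zero correlation with the post score, −r with the intended score) need no assumption beyond a linear regression. How far the reported correlations would be off depends on r, g, ρ and b, none of which the document gives. Over the ranges shown, a true 0.5 against an outcome measured once becomes anything from −0.35 to +0.33. For pairs measured twice it becomes 0.05 to 0.50 when the baseline correlation is between 0 and 0.5.

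The damage is confined to this correlation analysis. The tests of the intervention on outcomes that have a baseline do not use these scores and are unaffected.

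**What to change.** In Section G2, replace the sentence with wording such as:

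> For continuous variables measured at baseline and at the final assessment (sEMG, ultrasound, Kent imaging, DPN Check), the post-treatment score will be regressed on the pre-treatment score, and the residual will be used as the residualised change score.

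Then:

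1. Remove strength from that list and from the sentence about change from baseline. Analyse it as a between-arm comparison at the final visit. If the sponsor prefers a strength change score, F2 must schedule a baseline test and G2 must say how patients who cannot perform it are handled.
2. State that residualised sEMG change is correlated with the single values of final-visit strength and of the 1-month IADL, Life Space, KATZ and BAI scores. Adjustment of these correlations for arm is optional.
3. For consistency, reword the dynamometry part of Aim 2 H1.1 so that it refers to a final-visit comparison.

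The cost is two or three sentences in G2 and one phrase in Aim 2. No new data or visits are needed unless a baseline strength test is added.

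### The G2 correlations pool both arms without adjusting for randomised arm, so a shared therapy effect can look like sEMG tracking function; the change scores are also regressed in the reverse direction

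*Combined protocol and SAP*

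**What the plan says.** Section G2 (Data Analysis) puts the arm comparison in the mixed models or GEEs, which "will be used to test the intervention effect for each of the primary or secondary outcomes". A separate step follows. For all continuous variables, "pre-treatment scores will be regressed on post-treatment scores to form residualized change scores". The examples listed are sEMG, ultrasound, strength, Kent imaging and DPN Check. Then "Correlations will then be generated among these scores to determine whether changes in sEMG factors are related appropriately" to clinically assessed function and to self-reported activity one month after discharge. An ANOVA comes next: "ANOVA test will be used to examine significant difference between patients with severe risk factors for prolonged ICU stage (e.g. age, BMI, cardiovascular morbidities"). The paragraph ends: "Moderator effects will also be examined for exploratory purposes".

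Neither the correlation sentence nor the ANOVA sentence mentions arm, stratification by arm or a partial correlation. The covariate rule does not supply arm either: "Those descriptors which showed statistical significant difference will be considered as covariates for adjusting the results in the following assessments". That rule concerns baseline descriptors compared between the arms, and arm is not one of them. The moderator sentence names no moderator, model or interaction.

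Section F2 lists sEMG, muscle ultrasound, Kent imaging and DPN Check at baseline and follow-up. It lists ankle dynamometry only at the final visit, and the questionnaires only by telephone one month after discharge.

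**The concern.** A correlation pooled over two randomised arms mixes two things: the association between patients within an arm, and the separation of the arm means. If therapy raises both sEMG and a functional measure, the active patients sit higher on both axes, and a correlation appears even if sEMG says nothing about function among patients treated alike. The plan expects therapy to act on several measures at once: "We assume that a successful intervention is also helpful to maintain subjects muscle mass, reduce neuromyopathy signs and increase perfusion". The better the therapy works, the larger this contribution.

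This correlation is the step in G2 that asks whether sEMG change goes with function. The background section argues for sEMG as an objective measure in patients who cannot cooperate, and F1 says the sample is meant to explore objective measurement tools. A correlation produced only by the arm difference could be carried forward as support for sEMG as an outcome.

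The direction of the regression is a second defect in the same step. Regressing pre on post leaves the part of baseline not explained by the later value, which is not a change score in the usual sense and is scaled in reverse.

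**Working it through.** **Inputs from the documents.** N = 40, allocated 1:1, so 20 per arm (F1, G1). Significance rule: "P-values of 0.05 or less will be considered statistically significant based on a two-sided test unless otherwise noted" (G2). The sample is one of convenience. No effect size, SD or expected correlation is stated, so there is no figure of the plan's own to reproduce.

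**Assumptions.** Within-arm correlation between the two measures is zero. Therapy shifts the post score by d within-arm SDs. The pre-post correlation ρ is 0.3, 0.5 or 0.7. All 40 patients supply both scores. Rates come from simulation with 50,000 to 100,000 trials per setting.

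**1. Two measures shifted by arm, no residualising.** At 1:1 allocation,

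r = (d₁d₂/4) / √[(1 + d₁²/4)(1 + d₂²/4)].

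For d₁ = d₂ = 0.8: 0.16/1.16 = 0.14. For 1.0: 0.25/1.25 = 0.20. If one shift is zero, r = 0.

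**2. Residualised in the usual direction (post on pre).** Residualising removes baseline variance, so the shift in residual SDs is larger: d* = d/√(1 − ρ²). Example, d = 0.8 and ρ = 0.7: d*² = 0.64/0.51 = 1.255, and r = 0.314/1.314 = 0.24.

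| Shift on both measures | Mean pooled r, ρ 0.3 to 0.7 | P<0.05, pooled | P<0.05, arm-adjusted |
|---|---|---|---|
| 0.5 SD | 0.06 to 0.11 | 7-10% | 5% |
| 0.8 SD | 0.15 to 0.24 | 15-31% | 5% |
| 1.0 SD | 0.21 to 0.33 | 26-56% | 5% |
| 0.8 SD on one, 0 on the other | 0.00 | 5% | 5% |

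The arm-adjusted test has 40 − 2 − 1 = 37 degrees of freedom, against 38 for the pooled test.

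**3. Residualised as written (pre on post).** The slope is b = ρ/(1 + d²/4), and the arm shift in the residual is −bd, so its sign is reversed. For d = 0.8 and ρ = 0.7: b = 0.7/1.16 = 0.603. Between-arm variance is b²d²/4 = 0.058, within-arm variance is 1 − 2bρ + b² = 0.519, and r = 0.058/(0.058 + 0.519) = 0.10. For two such scores, P<0.05 occurs in 5-9% of trials at 0.8 SD and 5-12% at 1.0 SD.

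**4. sEMG against a one-month score with no baseline, both shifted 0.8 SD.** With post on pre, mean r is 0.14 to 0.18 and P<0.05 occurs in 14-20% of trials. With pre on post, mean r is −0.04 to −0.12 and P<0.05 occurs in 6-11%. A therapy that helped both measures would then appear as a negative association.

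**5. Risk-factor ANOVA.** With arm left out and the risk factor independent of arm, type I error is 4.9-5.0% at d = 0.8, 1.0 and 1.5, so there is no bias. If a continuous factor were grouped, at N = 40 and an assumed true correlation of 0.4, power would be 74% with the factor kept continuous, 53% with a median split and 46% with a top-quartile split.

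**The case against.** The strongest reply is that pooled and arm-adjusted correlations answer different questions. Whether sEMG change accompanies functional change across all patients, including change that therapy causes, is a fair descriptive question. That stands, and it is why the pooled figure may still be shown. It does not rescue the pooled figure as evidence that sEMG tracks function, because a shared arm effect alone can produce it.

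Second, the inflation depends on effect sizes that the documents do not give. It is small at 0.5 SD, absent if only one measure responds, and small under the wording as it stands. This also stands. But the small figure under the literal wording comes from a reversed regression, and correcting the direction without adding arm would restore the larger inflation.

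Third, the moderator sentence might be read as bringing arm in, since moderation of a treatment effect requires it. It names no model, and it does not govern the correlations.

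A reader might also infer that the risk-factor ANOVA suffers the same bias. It does not: a baseline risk factor is independent of randomised arm apart from chance, so leaving arm out costs only precision. Nor do the documents say that age and BMI will be split at the median or at any other point. Grouping is inferred from the choice of ANOVA, and no cut-point or dependent variable is stated.

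**Conclusion.** The point holds for the correlations and is minor in weight. G2 omits arm from the step meant to show that sEMG change relates to function, and it builds the scores in the reverse direction. With the direction corrected and arm still omitted, the chance of a spurious P<0.05 is about 7-10%, 15-31% and 26-56% at assumed shifts of 0.5, 0.8 and 1.0 SD on both measures. With arm in the model it is 5%. As written, the inflation is small, but the sign is wrong against one-month scores.

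These figures rest on 20 per arm, complete data, ρ of 0.3 to 0.7 and no within-arm association. A reader might conclude that the trial's treatment comparison is compromised. The documents do not support that: the intervention effect is tested in separate mixed models or GEEs, which this step does not touch. The ANOVA is a secondary matter of precision, and only if age and BMI are in fact grouped.

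**What to change.** - Where a baseline is listed (sEMG, ultrasound, Kent imaging, DPN Check), regress the post score on its own baseline plus arm and take the residuals. This corrects the direction and brings in arm together.
- Where no baseline is listed (dynamometer strength, the one-month questionnaires), adjust the single score for arm only, and do not call the result a change score.
- Report the arm-adjusted partial correlation with its confidence interval as the evidence on whether sEMG tracks function. Show the pooled correlation, if wanted, as description only.
- For the risk factors, name the dependent variable and use linear regression with arm and with age and BMI kept continuous.

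The cost is one model term and one degree of freedom per analysis, with no new data and no change to the mixed models.
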